#### E. Feasibility and Acceptability Data Collection Procedures

Feasibility and acceptability data will be collected throughout the study. We will track (a) rates of recruitment, protocol adherence and engagement, and retention; (b) adverse events; (c) participants', interventionists', and testers' perceptions of the intervention and/or study procedures (e.g., perceived benefits, burden, satisfaction); and (d) facilitators and barriers to successful completion of study procedures.

A number of methods will be employed to collect these data. Detailed records will be kept throughout the duration of the study. Planned documentation ranges from specifics of the screening and intake process to promotor notes summarizing each intervention session. We will hold fidelity checks periodically which will require the *promotor* audio/video record selected patient sessions with permission of the participant or for the supervisory OT or promotor to sit in on patient sessions. Additionally, a brief exit interview at the end of the fourmonth and 12-month assessment sessions will be administered to all participants. After the close of the fourmonth data collection, semi-structured focus groups and interviews will be held with participants and research staff, respectively. We will conduct two 1.5 to 2-hour participant focus groups (approximately eight people per group) that will be video recorded to allow for verbatim transcription and analysis. Participants who join a focus group will have completed the intervention, as well as all other study requirements, within the past month, and will be selected so as to achieve variation in sex, ethnicity, education level, and number of chronic diseases. Furthermore, one-hour exit interviews will be conducted with the treating *promotores*, supervising occupational therapist and promotor, and assessment battery deliverers. Interviews will be audio recorded to allow for verbatim transcription and analysis by one of our bilingual research team members authorized to interact with participants. Due to the semi-structured nature of the focus groups and interviews, the focus group facilitator or interviewer may depart from facilitation guides in order to probe for pertinent details and follow up on information disclosed by the participants.

#### F. Data Management and Storage and Communication

Data collection during assessment sessions will primarily occur within REDCap—a secure, web-based application designed to support data collection for research—using a study-specific laptop. In rare circumstances (e.g., upon loss of internet access, participant request), assessment data will be captured through use of hardcopy questionnaires. REDCap will also serve as a secure, password protected storage database for data collected during assessment sessions (not including interview/focus group data). Data that are captured in hard copy form, will be transferred to REDCap by authorized, trained study personnel. Any hard copies of study documents when not in use will be maintained and stored in locked files at the Antelope Valley study office during the recruitment and intervention implementation phases of the study. Documents containing participants' names (e.g., informed consent documents) will be stored and locked separately from documents with participant codes. All hardcopy files will be permanently transferred to the USC study office (CHP-101) upon completion of the post-intervention assessments and focus groups. Data that are neither captured within REDCap nor in hardcopy format (i.e., audio/video recordings), will be stored on a secure, password protected data server of USC.

Research investigators and staff located at USC and Antelope Valley will remain in regular communication throughout the study. At the outset of the study and at subsequent one-month intervals, a project staff meeting will be held. We will discuss items such as the safety and proper treatment of the research participants. These meetings will be mandatory for all project personnel who have contact with participants or with data that result from the study. Additionally, an internal committee comprised of the principal investigator, Antelope Valley collaborator [name], the co-investigator responsible for training and supervising the occupational therapist, and the project coordinator will meet monthly to assess participant recruitment; accrual and retention; data quality and timeliness; participant risk versus benefit; and the development of external conditions that could potentially affect

the study. Additionally, the primary investigator and collaborator [name] will remain in regular weekly contact via telephone or email to discuss any study-related issues that arise.

# **III. Statistical Considerations**

# A. Sample Size

We will enroll 40 participants in this pilot study. With this sample size we will have 80% power to detect a statistically significant change score effect size of 0.454 in any of our continuous outcome variables (two-sided alpha=0.05, paired sample t-test). This is considered a medium effect size. In the Well Elderly 2 study, effect sizes were generally small. Therefore, we expect this pilot study to have minimal statistical power. Nevertheless, this sample size is adequate for assessing the feasibility and acceptability of this intervention and to identify any obstacles that need to be addressed before a large-scale version of this study can be undertaken.

# B. Data Analysis

**Specific Aim 1:** Through a mixed-methods process evaluation, assess the feasibility and acceptability of the *¡VMV!* intervention and associated study procedures, as administered in a community-based health service system.

Feasibility and acceptability will be determined by (a) analyzing rates of recruitment, protocol adherence and engagement, and retention; (b) monitoring adverse events; (c) examining participants' and interventionists' perceptions of the intervention and study procedures (e.g., perceived benefits, burden, satisfaction) as collected during focus groups and interviews; and (d) identifying facilitators and barriers to successful completion of study procedures. Focus group and interview transcripts will be analyzed using a qualitative descriptive approach. Two researchers will independently code translated transcripts. During this data analysis phase, they will meet biweekly for three months to review codes and discuss emerging themes. Each researcher will highlight significant transcript passages and their codes at analytic meetings, during which codes will be refined and preliminary themes identified. The review of relevant interview passages and thematic organization of findings will be an iterative process that will continue until consensus is achieved among the research team. Once the team agrees upon the primary themes expressed during the interviews and focus groups, one researcher will extract excerpts that support each theme. Data from the focus groups and interviews will be compared and contrasted to other data tracked throughout the study by the research team and interviews (e.g., adherence, participant engagement).

# *Specific Aim 2: Preliminarily examine the efficacy of the ¡VMV! intervention to improve patient-relevant outcomes pertaining to diabetes and CVD risk and general health promotion.*

Efficacy of the intervention will be preliminarily evaluated based on comparison of baseline and post-intervention data collected on the following outcomes: perceived clinical outcomes related to symptoms, activity, and wellbeing (MYMOP2), pain (BPI Pain Severity and Pain Interference subscales), dietary intake (Block Food Frequency Questionnaire), dietary habits (My Habits Scale), self-reported exercise (IPAQ), sleep quality (PSQI), satisfaction with participation (PROMIS Satisfaction with Participation in Discretionary Social Activities and Satisfaction with Participation in Social Roles short forms), depression (PROMIS Emotional Distress -Depression – Short Form 8a), stress (Elo et al.'s Single Item Stress Index), patient activation (PAM-13), clinical outcomes (HbAlc, lipid profiles, waist and hip circumference, waist to hip ratio), CHD risk (Framingham Risk Score LDL Points Total), diabetes risk (EPIC Diabetes Risk Score), and healthcare service utilization.

Data will be directly entered into the Research Electronic Data Capture (REDCap) system. Data will be checked for completeness and reasonableness. Descriptive statistics will be presented and analyses will inform the appropriateness of our intended statistical plan. Changes in outcome variables will be assessed using paired-sample t-tests. Baseline covariates (e.g., age, gender), will be assessed for effect modification. Results will be stratified by any effect modifiers, and repeated measures ANOVA will be used to adjust for confounders. These preliminary estimations will inform refinement of the outcomes assessment battery and sample size calculations for a subsequent large-scale trial.

*Specific Aim 3:* Based on data collected from Aims 1 and 2, refine and optimize the lifestyle intervention to prepare for a large-scale randomized controlled trial.

Our multidisciplinary team will use the triangulated quantitative and qualitative data resultant from specific aims 1 and 2 to make important refinements necessary to improve the overall feasibility, acceptability, and efficacy of the intervention. We will fine tune data collection procedures as needed to ensure that participants can complete the assessment battery thoroughly and comfortably. Questions with excessive missing data will be re-evaluated. Questionnaires will be checked for internal consistency and ceiling and floor effects and will be revised accordingly. Aim 3 will be complete when: (a) there are no remaining questions/concerns from the investigative team about the *¡VMV*! intervention or study procedures; (b) modifications to the intervention and study procedures deemed necessary have been successfully integrated; and (c) a finalized research protocol has been produced.

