#### **II.** Methods

#### A. Study Design

In the proposed study, 40 Latino adults aged 50-65 years old will be included. All participants will receive the intervention. Throughout the course of their study involvement, participants will continue to receive usual care at their regular primary care facilities or community health clinics or from community-based programs in which they are enrolled.

An assessment battery, consisting of both questionnaire and clinical outcome measures, will be administered at baseline, a subsequent four-month post-testing session, and a 12-month follow-up testing session. Each assessment period will include an in-person assessment to obtain clinical values and responses to questionnaires. Each in-person assessment period is expected to last about 1.5 to 2 hours. In addition to study-generated measures, we will collect electronic data on medical service utilization and clinical assessments from our collaborating healthcare partners. Finally, at the conclusion of the intervention and post-testing, we will collect information about implementation issues, including reach, patient and staff satisfaction, identification of intervention facilitators and barriers, and program sustainability.

Total length of enrollment will include one day for initial testing, four months for the intervention, one day for follow-up testing post-intervention, one day if the person participates in a post-intervention focus group, and one day if the person participates in the 12-month follow-up testing session.

B. Participants, Recruitment, and Consent

2.

A convenience sample of 40 late middle-aged (50-65 years old) Latino adults will be recruited from direct personal contacts at recruitment tables, provider referrals, and postings at the Antelope Valley Community Clinic and local community centers. If a potential participant responds to a flyer and calls a study team member, the screening form will be utilized to describe the study and ensure his/her eligibility. For those individuals who participated in the study as a supervisor, intervener, or tester, research staff will directly approach them to solicit participation in a follow-up interview.

Potential participants for the intervention and follow-up focus group will be included if they:

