Although at the outset of the intervention patients will be assigned to groups of ten, the first session will be individualized and, in most cases, home-based. In this session, led by both the *promotor* assigned to the patient's group and an occupational therapist who will be present via teleconference using HIPAA compliant VSee software, the patient will be able to review a personalized Health Status Report, which contains a summary of the most recent information extracted from his or her health records, including health markers such as weight and blood pressure levels. After discussing this report, the patient, occupational therapist, and promotor will develop a Health Action Plan (HAP). The HAP will include three health-related goals that the patient wishes to achieve through the intervention and a list of four to five strategies or activities that can be implemented to achieve these goals. Additionally, each participant will be given a wrist-worn activity monitor to keep permanently even after the intervention concludes. Participants will be instructed in the features of the monitor and guided in how they

could use it to help achieve the goals delineated in the HAP, as appropriate. Through ongoing individual and group supervisory meetings, the occupational therapist will use the information from the HAP to guide the *promotor* in tailoring the intervention to meet individual patient's needs.

During the course of individual, group, and phone sessions, the HAP will be updated with topic-specific unit content. At the beginning of month three, the *promotor* will take note of the progress that the patient has made toward his or her goals and reassess various health indicators such as weight or blood pressure. These results will be forwarded to the patient's physician. Concurrently, patients will be encouraged to review these results to self-monitor any change in their health status. By the conclusion of the intervention, each patient will be helped to adopt his or her HAP to maximize the likelihood of lifelong implementation of health-enhancing activity and habits.

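### Aim 2 treats an uncontrolled before-after change as efficacy, so any background drift counts as programme effect and can carry into the size of the later RCT

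*Combined protocol and SAP*

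**What the plan says.** The design has a single arm. Section II.A states "All participants will receive the intervention" and adds that participants keep their usual care throughout. Section III.A gives the size, "We will enroll 40 participants in this pilot study", and the precision: "80% power to detect a statistically significant change score effect size of 0.454" ("two-sided alpha=0.05, paired sample t-test"). It notes that effects in an earlier study of the parent programme were generally small, and says "we expect this pilot study to have minimal statistical power".

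Section III.B, Specific Aim 2, sets the contrast: "Efficacy of the intervention will be preliminarily evaluated based on comparison of baseline and post-intervention data collected on the following outcomes". Changes are tested with paired t-tests. Baseline covariates are examined as effect modifiers, and repeated measures ANOVA is used to adjust for confounders. The section then says that the estimates will inform the sample size of a later large trial.

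On record data, section II.A says "we will collect electronic data on medical service utilization and clinical assessments from our collaborating healthcare partners". The extraction described under Healthcare Service Utilization in section II.C covers utilization only, over the six months before baseline and at the end of the intervention. Section II.D uses record values in a Health Status Report for the first session: "a summary of the most recent information extracted from his or her health records, including health markers such as weight and blood pressure levels".

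**The concern.** A paired t-test has mean change of zero as its null hypothesis. That null matches 'the programme did nothing' only if the same patients would not have changed, on average, over the same four months without it. Nothing in the plan supports this condition. There is no untreated group, run-in or external comparator. Adjusting for baseline covariates does not supply an untreated time course.

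The documents themselves give reasons to expect some background change. Usual care continues. Some participants come through provider referral. MYMOP2 asks each participant to name symptoms that bother them at baseline and then rates those same symptoms again, which invites regression to the mean. MYMOP2 is also the instrument that section II.C names as the secondary outcome.

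Two things are at stake. First, a significant change could be read as evidence that the programme works, at an error rate well above the nominal 5%. Second, if the uncontrolled change becomes the expected between-group difference in the next trial, that trial will be too small.

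**Working it through.** **Inputs.** n = 40, two-sided alpha 0.05, paired t-test and detectable effect 0.454 at 80% power (section III.A); one treated arm (section II.A); paired test of change (section III.B). The drift sizes are assumptions, because the documents give none.

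**Formula.** For a mean change of d change-score SDs, the test statistic follows a noncentral t distribution with 39 degrees of freedom and noncentrality d × √40 = 6.325 × d. The critical value is 2.023. The rejection probability is P(T > 2.023) + P(T < −2.023).

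**The plan's own figure.** At d = 0.454 the noncentrality is 2.871 and power is 79.96%. Solving for exactly 80% gives d = 0.4543. The stated figure reproduces, assuming that all 40 provide both measurements.

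**No programme effect, background drift only.** The same formula applies with d as the drift:

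| Drift (change-score SD) | Noncentrality | Tests with p<0.05 |
|---|---|---|
| 0 | 0 | 5.0% |
| 0.1 | 0.632 | 9.5% |
| 0.2 | 1.265 | 23.5% |
| 0.3 | 1.897 | 45.7% |
| 0.454 | 2.871 | 80.0% |

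The last row repeats the power calculation. A drift as large as the effect that the study is sized to detect is declared significant as often as a real effect of that size.

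**Units.** These are SDs of the change score. The change-score SD equals √(2 − 2r) outcome SDs when variances are equal and r is the baseline-to-post correlation. With an assumed r = 0.7 it is √0.6 = 0.775, so a drift of 0.2 outcome SD is 0.2/0.775 = 0.258 change-score SD. The rejection rate is then 36% instead of 23.5%.

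**Effect on the next trial.** Required sample size is proportional to 1/(effect)². If the observed change is a true effect δ plus drift b, and δ + b is used for planning, the trial gets (δ/(δ + b))² of the size it needs. With b = δ (an illustration) that is (1/2)² = one quarter.

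**Could record values correct for drift?** Take one earlier record value per patient and compare (post − baseline) with (baseline − earlier). With equal spacing, variances and correlations (assumed), the variance of this contrast is 6 − 8r + 2r = 6 − 6r, against 2 − 2r for the simple change. The SD ratio is √3 = 1.73. The detectable effect rises from 0.454 to 0.787 change-score SD, and power at 0.454 falls from 80% to 37%. If only 30 or 20 patients had a usable record value, the detectable effect would be 0.92 or 1.14. At this sample size such values could serve only as description.

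**The case against.** The strongest reply is that the plan does not overclaim. Aim 2 is labelled preliminary, section III.A concedes minimal power and rests the sample size on feasibility and acceptability, and an RCT is to follow. No success rule or go/no-go decision depends on a p-value from Aim 2. Asking a declared single-arm pilot for a control group would be a preference about design.

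Much of this stands, and no control group is asked for here. But low power and a preliminary label concern precision, whereas drift is a bias that more patients would not remove. The estimates also have a stated later use, in sizing the next trial.

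A reader might also infer that the plan collects record values which would reveal each patient's earlier trend, and then leaves them unused. The documents do not support that:

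- Record values are used, in the Health Status Report; what is missing is a role in the Aim 2 analysis.
- Entry requires one primary-care visit in the past year, which guarantees neither a measurement nor the two values that a trend needs.
- The six-month look-back is stated for utilization only.
- The record markers named as examples, weight and blood pressure, are not in the Aim 2 outcome list, and most listed outcomes are questionnaires with no record counterpart.
- A slope from earlier months would not isolate season or the effect of retesting.

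**Conclusion.** The point holds for the inference drawn from Aim 2. In this design a paired test against zero cannot separate programme effect from background change. With no programme effect, the chance of p<0.05 per test is 9.5% to 80.0% for drifts of 0.1 to 0.454 change-score SD. This rests on 40 complete pairs, the paired t model, and drift sizes that are assumed and not taken from the documents. It does not show that drift of any given size will occur, and it casts no doubt on the plan's power figure or on n = 40.

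The record data are a smaller matter of specification. Section II.A announces clinical assessments from healthcare partners, and the Aim 2 analysis gives them no role. Whether they could show an earlier course cannot be judged from the documents, and displaying them would leave the percentages above unchanged.

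**What to change.** In section III.B, Specific Aim 2:

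1. Describe the results as within-person change from baseline, with 95% confidence intervals, and state that no conclusion about efficacy will be drawn from them. With 40 pairs the interval is the mean change ± 2.023/√40 = ± 0.32 change-score SD.
2. State that the uncontrolled mean change will not be taken as the expected between-group effect when the later RCT is sized. Variability and retention estimates can still be used for that purpose.
3. State what the record-based clinical assessments announced in section II.A are for. If it is only the Health Status Report, say so. Optionally, if dated values from before baseline exist, show them descriptively with the number of patients contributing and without a test.

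Items 1 and 2 need a few sentences and no change to sample size, visits or treatment. Their cost is a more modest Aim 2 claim, and the later trial will need its expected effect from another source. The optional display in item 3 would add extraction work on values that may be irregular or absent, and it would not cover the questionnaire outcomes.

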# C. Assessment Procedures

Following the informed consent process, participants will complete a battery of self-report questionnaires and clinical tests. The following data, with the exception of fixed background variables, will be assessed during each measurement point (baseline, four months, and 12 months). Participants may undertake assessment in Spanish or English, as preferred.

*—Background*. Information regarding participants' background and demographics (e.g., sex, race, smoking status, insurance coverage) will be collected using a study-specific questionnaire. Additionally, ongoing health problems will be documented (i.e., a checklist will include selected health conditions such as cancer, heart attack, heart failure, hypertension, high cholesterol, arthritis, asthma, alcohol abuse, drug abuse, mental/psychiatric problem, other).

*—Measure Your Medical Outcome Profile 2* (MYMOP2). The MYMOP2 is a simple patient-centered questionnaire that asks the participant to identify one or two symptoms that are bothersome. Patients rate the severity of the symptoms as well as how much they interfere with their daily activities. Upon retest, participants are asked about the symptoms that were initially identified, but are not told what their initial ratings were. The questionnaire has been shown to be sensitive to change, and has demonstrated construct  and criterion validity. Most importantly, this short item questionnaire gets to the heart of what is important to the patient and measures the personally relevant effect of changes that have taken place over the measurement interval. Therefore, the mean degree of change across the set of self-reported symptoms on the MYMOP2 will be used as the study's secondary outcome.

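### Aim 2 promises confounder adjustment by repeated measures ANOVA, but in an all-treated before-after design baseline covariates leave the mean change unadjusted, and the estimates go forward to RCT sizing without restriction

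*Combined protocol and SAP*

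**What the plan says.** All places are in the combined protocol and SAP.

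- **II.A Study Design.** There is one group of 40: "All participants will receive the intervention". Care outside the study goes on: "participants will continue to receive usual care at their regular primary care facilities".
- **III.B, Specific Aim 2, contrast.** "Efficacy of the intervention will be preliminarily evaluated based on comparison of baseline and post-intervention data", over a long list of outcomes that includes healthcare utilisation.
- **III.B, Specific Aim 2, methods.** "Changes in outcome variables will be assessed using paired-sample t-tests". Then: "Baseline covariates (e.g., age, gender), will be assessed for effect modification". Results are to be stratified by any modifiers found, after which "repeated measures ANOVA will be used to adjust for confounders. These preliminary estimations will inform refinement of the outcomes assessment battery and sample size calculations". The trial to be sized is described in the Aim 3 text as randomised and controlled. No confounder is listed.
- **III.A Sample Size.** 40 participants give "80% power to detect a statistically significant change score effect size of 0.454" (paired t-test, two-sided 0.05). The same section says that effects in the earlier Well Elderly 2 study were generally small and that power will be minimal.
- **II.C Assessment Procedures.** MYMOP2 "asks the participant to identify one or two symptoms that are bothersome" and follows those same symptoms at retest.

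**The concern.** The wording tells a reader that a modelling step will deal with confounding of the efficacy estimates. In this design, exposure to the intervention and the passage of time are the same contrast. The covariates the plan gives as examples are baseline ones. A covariate with the same value before and after can modify a change, but it cannot confound the overall mean change.

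What can bias that change is whatever else moves between the visits: secular trend, repeat testing and, for symptoms picked because they are troublesome at baseline, regression to the mean of unknown size. Listing more baseline confounders would not help.

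Two things are at stake. An Aim 2 estimate could be reported as adjusted while still carrying all of the uncontrolled change. That estimate could then enter RCT planning as if it were a between-group effect.

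**Working it through.** **1. The plan's own figure.** Inputs from III.A: n = 40, standardised change 0.454, two-sided alpha 0.05, paired t-test. Noncentrality = 0.454 × √40 = 2.871 on 39 df, giving power 79.96%. The stated 80% reproduces.

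**2. What adjustment for a baseline covariate does.** Code time t = 0 before and 1 after, and let x_i be a covariate fixed at baseline.

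- *Main effect.* Over complete pairs, the cross-product of time and covariate is Σ_i (x_i − x̄)(−0.5 + 0.5) = 0. Time and covariate are orthogonal, so the fitted time effect is mean(after) − mean(before), the same as the paired mean change.
- *Covariate by time, mean-centred.* The model for the change is d_i = δ + γ(x_i − x̄) + e_i. The centred term sums to zero, so the estimate of δ is again the mean of d_i.

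Adjusted minus unadjusted is therefore 0 in both forms. The estimate targets τ + s, where τ is the intervention effect and s is any change that would have occurred anyway.

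**3. Numerical check.** Simulated all-treated pairs, n = 40, 4,000 replicates, adjusting for centred age and sex. The values of τ and s are assumed.

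| Assumed τ | Assumed s | Mean change, unadjusted | Mean change, adjusted |
|---|---|---|---|
| 0.2 | 0.254 | 0.457 | 0.457 |
| 0 | 0.254 | 0.257 | 0.257 |

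The largest difference between the two estimates in any replicate was about 2 × 10⁻¹⁵, which is rounding error. Adjustment removed none of s.

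**4. What can and cannot be separated.** Forty subject columns plus one time (intervention) column have rank 41. Adding a factor that moves identically for everyone, such as a common trend or a common repeat-testing effect, leaves the rank at 41, so it is not separable from the intervention. Adding person-level utilisation, which varies between people at each time, raises the rank to 42, so that factor is separable.

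**5. Illustration for the RCT.** This assumes that the pilot mean change is used as the between-group target difference. It also assumes that a fraction f of a 0.454 change is not due to the intervention; the documents give no figure for f. Two-sample t-test on change, SD of change = 1, two-sided 0.05, 80% power. The approximation is n per arm ≈ 2(1.960 + 0.842)²/Δ² = 15.70/Δ²; the t-test solution is about one higher.

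| f | Δ = 0.454(1 − f) | t-test n | Per arm | Power with 78 per arm |
|---|---|---|---|---|
| 0 | 0.454 | 77.1 | 78 | 80% |
| 10% | 0.409 | 95.0 | 95 | 72% |
| 25% | 0.341 | 136.4 | 137 | 56% |
| 50% | 0.227 | 305.6 | 306 | 29% |

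**6. Precision of the outputs that remain sound.** With n = 40, the 95% interval for an SD runs from √(39/χ²₀.₉₇₅) to √(39/χ²₀.₀₂₅), or 0.82 to 1.28 times the estimate. Sample size goes with the square of the SD, so it varies from 0.67 to 1.65 times. These outputs should be carried forward with intervals.

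**The case against.** The best reply has five parts.

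- **Age and gender are named for effect modification, not as confounders.** Correct. The adjustment may be meant for the stratified comparisons, where a baseline covariate can confound a difference in change between subgroups. That use is legitimate and should be kept. It does not rescue the overall change, and the text does not confine the adjustment to subgroups.
- **Usual care is not the same as time.** Also correct. A reader might infer that no model on these data could separate usual care from the intervention. The documents do not support that: II.C collects utilisation per person, so partial adjustment is possible. But the plan names no such covariate, and utilisation is itself an Aim 2 outcome. The program also has a healthcare navigation unit (Table 2), so utilisation may lie on the intervention's own pathway.
- **Complete pairs are not guaranteed.** True. With dropout related to a baseline covariate, a model using that covariate can correct for who was lost. That addresses missing data, not uncontrolled change.
- **The plan does not say that the mean change will size the RCT.** True. A reader might infer that it will, since the estimates are passed on without restriction straight after the change analyses. That is an inference, and 0.454 is a detectable effect, not an expected one. A reader might also infer that the ANOVA costs power through its covariate coding. The plan specifies no coding, so no such loss can be claimed.
- **This is a pilot with efficacy labelled preliminary.** It is, III.A is candid about power, and III.B says analyses will inform whether the intended plan is appropriate. Low power concerns precision, however. Nothing says that the change is not attributable to the intervention, and the adjustment clause points the other way.

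**Conclusion.** The point holds in a limited form. For the overall baseline-to-post change, adjustment for baseline covariates alters the estimate by exactly 0 with complete pairs, and trend, repeat testing and regression to the mean stay in it. The plan therefore claims a property that its design cannot deliver, and no list of baseline confounders would change that. Partial adjustment for a measured time-varying factor is possible but unspecified. Baseline covariates keep a proper role in subgroup comparison and in handling dropout.

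The 78 against 95, 137 or 306 per arm is illustration only, resting on an assumed use of the mean change and an assumed share of non-intervention change. The 80% power, Aim 1, and the pilot's SDs, correlations and retention are unaffected. The change is worth making because it alters what Aim 2 may conclude.

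**What to change.** In III.B, Specific Aim 2, keep the stratification by effect modifiers and replace the clause on adjusting for confounders with:

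> *Repeated measures models with mean-centred covariates may be used to describe effect modification, to compare subgroups and to account for incomplete follow-up. Because all participants receive the intervention, baseline-to-post change is uncontrolled and will not be described as confounder-adjusted or attributed to the intervention.*

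Keep the sentence on use of the estimates and add:

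> *For RCT sample size the pilot will supply SDs, baseline-to-follow-up correlations and retention, with confidence intervals; the pilot mean change will not by itself be used as the between-group target difference.*

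This is a text change only, with no new data, visits or participant burden. The cost is that the pilot reports no adjusted efficacy estimate. The RCT target difference must also be justified from another source, which may make that trial larger.
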